5.2.2.2 Management of Increased Transaminases

Increased transaminases should be evaluated to determine whether confounding factors exist, such as metastatic lesions or biliary obstruction. For cases where treatment-related

increases are likely, dose modifications may be made with investigator discretion in consideration of clinical factors. Suggested recommendations are shown in Table 8.

Table 8: Treatment Modification for Increased Hepatic Transaminase

Toxicity	Treatment Delay	Dose Modification
Grade 1 (> ULN to 3.0 × ULN)	May be implemented based on Investigator and patient discretion	
Grade 2 (> 3.0 to 5.0 × ULN)	Not required	Decrease by 1 dose level
Grade 3/4 (> 5.0 × ULN)	Hold until ≤ Grade 1 or return to baseline	Decrease by at least 2 dose levels for a first dose reduction; decrease by at least 1 dose level if dose is already reduced.

5.2.2.3 Management of Hy's Law Cases

In the event a patient develops concurrent increase in AST and/or ALT $\geq 3 \times$ ULN, bilirubin $\geq 2 \times$ ULN but without concurrent increases in alkaline phosphatase (i.e., alkaline phosphatase $< 2 \times$ ULN), that is not attributable to liver metastases or biliary obstruction, investigational study treatment should be permanently discontinued.

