4.1 Inclusion Criteria

Patients must meet all of the following inclusion criteria to be eligible for enrollment into the study:

1. Histologically confirmed NSCLC with metastatic or unresectable, locally advanced disease.
2. Receipt of at least one prior platinum-containing chemotherapy or licensed immunotherapy regimen in the advanced disease setting.
3. Molecular analysis of patient-derived samples using a Sponsor- approved method and laboratory that demonstrates a genetic alteration activating *MET* in tumor tissue and/or ctDNA. If eligibility is established using a Sponsor-approved local laboratory, a tumor tissue specimen and/or blood sample is expected to be available for retrospective sequencing in the central laboratory selected by the Sponsor.
4. Measurable disease, as per RECIST version 1.1.
5. Eastern Cooperative Oncology Group (ECOG) performance status 0, 1, or 2 (Appendix 1).
6. Adequate bone marrow and organ function demonstrated by:
 - a. Absolute neutrophil count $\geq 1,000/\text{mm}^3$ ($\geq 1.0 \times 10^9/\text{L}$)
 - b. Alanine aminotransferase (ALT) and aspartate aminotransferase (AST) $\leq 2.5 \times$ Upper Limit of Normal (ULN), or $\leq 5.0 \times$ ULN for patients with documented liver metastases. Alkaline phosphatase levels $\leq 2.5 \times$ ULN. In the presence of extensive bone metastases, there is no upper limit for alkaline phosphatase.
 - c. Total bilirubin $\leq 1.5 \times$ ULN or $\leq 3.0 \times$ ULN for patients with Gilbert Syndrome or documented liver metastases.
7. ≥ 18 years of age.
8. Women of child-bearing potential (WOCBP) or men whose partner is a WOCBP agrees to use contraception while participating in this study, and for a period of 6 months following termination of study treatment.

9. Completed informed consent process, including signing IRB/EC-approved informed consent form.
10. Willing to comply with clinical trial instructions and requirements.

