5.2.1 Dose Modification

Study treatment-related adverse events that are intolerable or severe will be managed by treatment interruption and/or dose reduction depending on the circumstance. In response to observed toxicity, daily doses should be reduced by steps of at least 15-20% within the constraints of the available capsule or tablet dose strengths. Necessary dose reductions will typically be made in sequential steps but, under some circumstances, dose reduction by two steps (i.e., 30-40%) may be advisable and may be considered in consultation between the investigator and Sponsor (See Table 5 and Table 6). Dose reductions below the current guidelines may be allowed after consultation between the investigator and Sponsor. Patients requiring greater than 3 weeks to recover from drug-related toxicity should be considered for discontinuation from study treatment.

Table 5: Dose Adjustment Guidelines Soft Gel Formulation

Soft Gel - Capsule Formulation		
Dose Level	265 Daily Dose (BID Dose)	Number of capsules (150 mg capsule strength)
0 (Starting Dose)	2100 mg (1050 mg BID)	14 total (7 BID)
-1	1800 mg (900 mg BID)	12 total (6 BID)
-2	1500 mg (750 mg BID)	10 total (5 BID)

Table 6: Dose Adjustment Guidelines Spray Dried Dispersion Formulation

Spray Dried Dispersion – Tablet Formulation		
Dose Level	265 Daily Dose (BID Dose)	Number of tablets (100 mg and 250 mg tablet strength)
0 (Starting Dose)	1500 mg (750 mg BID)	6 total (3 BID) [3-250 mg BID]
-1	1200 mg (600 mg BID)	6 total (3 BID) [2-250 mg BID; 1-100 mg BID]
-2	1000 mg (500 mg BID)	4 total (2 BID) [2-250 mg BID]

Dosage interruptions to assess or treat intercurrent illnesses are allowed as needed in the judgment of the investigator.

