8.2.1 Laboratory Abnormalities

An abnormal laboratory test results should be reported as an AE in the CRF only if it is associated with one or more of the following:

- Clinical symptoms;
- Requires additional tests (beyond repeats), treatment or intervention;
- Results in change in study treatment dosing;
- Requires discontinuation from study treatment; and/or
- Considered by the investigator or Sponsor to be an AE.

Hy's Law

Hepatic function abnormality defined by an increase in AST and/or ALT to $\geq 3 \times$ ULN concurrent with an increase in total bilirubin to $\geq 2 \times$ ULN but without increase in alkaline phosphatase (i.e., alkaline phosphatase $< 2 \times$ ULN) meets the criteria for Hy's Law and raises the concern for drug-induced liver injury when no other cause of the abnormal laboratory results is identified. Follow-up investigations and inquiries will be initiated promptly by the investigational site to determine whether the findings are reproducible and/or whether there is objective evidence that clearly supports causation by a disease (e.g., cholelithiasis and bile duct obstruction with distended gallbladder) or an agent other than the investigational product.

Cases meeting Hy's Law should be reported as SAEs. Study drug should be permanently discontinued for a Hy's Law case.

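### Neither Hy's Law section requires MGCD265 to be held during the work-up, and the two sections do not match on which causes excuse the permanent stop

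*Combined protocol and SAP*

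**What the plan says.** Four places in the protocol bear on dosing when this pattern appears.

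- **Section 5.2.2.3 (Management of Hy's Law Cases).** For a patient who develops AST and/or ALT ≥ 3 × ULN with bilirubin ≥ 2 × ULN and alkaline phosphatase < 2 × ULN, the only action concerns a pattern "that is not attributable to liver metastases or biliary obstruction, investigational study treatment should be permanently discontinued".
- **Section 8.2.1 (Laboratory Abnormalities, Hy's Law).** It uses the same thresholds and says that values meeting them satisfy Hy's Law. A clause ties the suspicion of drug-induced liver injury to the absence of another identified cause. Follow-up "will be initiated promptly by the investigational site to determine whether the findings are reproducible" and "whether there is objective evidence that clearly supports causation by a disease" or by another agent. It ends: "Study drug should be permanently discontinued for a" Hy's Law case. That sentence states no exception.
- **Section 5.2.2.2 and Table 8 (Increased Transaminases).** Where a treatment-related rise is likely, "dose modifications may be made with investigator discretion in consideration of clinical factors". At AST/ALT > 3.0 to 5.0 × ULN the suggested step is "Decrease by 1 dose level", and no treatment delay is called for. Above 5.0 × ULN a hold is suggested. Bilirubin is not mentioned.
- **Sections 5.2.1 and 5.2.2 (with Table 7).** "Dosage interruptions to assess or treat intercurrent illnesses are allowed as needed in the judgment of the investigator". Treatment-related toxicity of Grade 3 or higher should be managed with an interruption. Below Grade 3, delay is left to the investigator and patient.

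Sections 5.2.2.3 and 8.2.1 do not refer to each other, and Table 8 refers to neither.

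**The concern.** When the pattern first appears, the site must decide whether to give the next dose while the cause is unknown. The stop in 5.2.2.3 turns on an attribution that has not yet been made. Section 8.2.1 orders the investigation that would make it, but sets no deadline and states no interim hold. From Cycle 3, scheduled chemistry falls only on Day 1 of each 21-day cycle. Unscheduled tests are expected (Table 2 preamble, Section 7.4.3), but no repeat interval is given.

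Two opposite errors are possible. A site that goes by Table 8 could continue at a reduced dose while drug-induced liver injury is still being ruled out. A site that takes the last sentence of 8.2.1 on laboratory values alone could end treatment for good on an unrepeated result, or in a patient whose liver metastases 5.2.2.3 would excuse. What is at stake is patient safety and avoidable loss of treatment.

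**Working it through.** No arithmetic tests this point. The check sets the texts against the same patient.

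**1. Two readings of Section 8.2.1.** Reading A: the laboratory values alone make a Hy's Law case. Reading B: the clause on no other cause is part of what makes a case. The text supports either.

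**2. Outcome for one illustrative patient** with AST 4 × ULN, bilirubin 2.5 × ULN and alkaline phosphatase below 2 × ULN:

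| State of the work-up | 5.2.2.3 | 8.2.1, reading A | 8.2.1, reading B |
|---|---|---|---|
| Cause not yet known | Attribution not made; no hold stated | Permanent stop | Work-up; no dosing instruction |
| Liver metastases or biliary obstruction | No stop | Permanent stop | No stop |
| Another disease or a concomitant medicine | Permanent stop | Permanent stop | No stop |
| Not reproduced on repeat | Not addressed | Permanent stop | Consequence not stated |

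No column contains a temporary hold. In the second row 5.2.2.3 conflicts with reading A; in the third it conflicts with reading B. So the excusing causes fail to match whichever reading is taken. The third row can arise in practice, because Section 5.4.1 lets patients continue ongoing medicines.

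**3. Does other text fill the first row?**

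- Section 5.2.2 and Table 7 call for interruption only for toxicity that is Grade 3 or higher and considered treatment-related. AST of 4 × ULN is Grade 2 in Table 8, and relatedness is the open question.
- Table 8 applies where a treatment-related rise is likely, and it is discretionary. At this AST it suggests one dose level down (750 to 600 mg BID for SDD tablets, Table 6) without a delay.
- Section 5.2.1 permits interruption but does not require it.

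Holding is therefore allowed and not required. Above 5 × ULN Table 8 does suggest a hold, so the practical gap is AST/ALT of 3 to 5 × ULN with the bilirubin and alkaline phosphatase criteria met.

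**4. Overlap with baseline values.** Inclusion criterion 6 against the trigger, for a patient with documented liver metastases:

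| | Allowed at entry | Trigger | Overlap |
|---|---|---|---|
| AST/ALT | ≤ 5.0 × ULN | ≥ 3 × ULN | 3.0 to 5.0 |
| Total bilirubin | ≤ 3.0 × ULN | ≥ 2 × ULN | 2.0 to 3.0 |
| Alkaline phosphatase | ≤ 2.5 × ULN | < 2 × ULN | < 2.0 |

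The bilirubin limit of 3.0 × applies to "ULN for patients with Gilbert Syndrome or documented liver metastases". An eligible patient can thus meet the pattern before the first dose. In 5.2.2.3 the pattern must develop, which partly excludes such values, but a mandatory hold needs to say so explicitly.

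**5. Size.** Section 1.2.3 gives related AST increase 25% and ALT increase 20%, with Grade 3 at 2% each. It gives no figure for bilirubin increase or for the combined pattern, so the number affected cannot be estimated.

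**The case against.** The strongest reply is that 5.2.2.3 can be read as a stop by default: an unexplained pattern has not been attributed to metastases or obstruction, so treatment ends. It is also the more specific rule and directly follows the discretionary Table 8. Under reading A, 8.2.1 likewise gives an immediate instruction. On these readings there is no interval without guidance, and an experienced investigator would probably hold anyway.

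Part of this stands. The plan does not tell sites to keep dosing, and interruption is open to them throughout. If another value, such as bilirubin, reached Grade 3 and was judged treatment-related, Section 5.2.2 would call for interruption, which narrows the gap further.

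It does not remove the point. Stop by default means a permanent stop before the repeat test and work-up that 8.2.1 requires can count, so the work-up loses its role in dosing. The alternative readings leave the interval uncovered. The text does not settle which applies.

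A reader might go further and infer both that 8.2.1 gives no dosing instruction during the work-up and that it makes the stop independent of cause. The documents do not support the two together: the first needs reading B and the second needs reading A. What holds on either reading is that neither section states a temporary hold and that the excusing causes do not match.

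**Conclusion.** The point holds as a patient-safety wording gap. No required hold covers the work-up, and 5.2.2.3 and 8.2.1 excuse different causes, so two sites following the text could treat the same patient differently. The gap matters in practice at AST/ALT of 3 to 5 × ULN with bilirubin ≥ 2 × ULN and alkaline phosphatase < 2 × ULN. The number of patients is unknown and may be very small.

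Two inferences should be avoided. Subtracting Grade 3 from all related rises (25% − 2% = about 23% for AST, 20% − 2% = about 18% for ALT) might look like a measure of exposure to the gap. It is not: these rises are counted without regard to bilirubin, and Grades 1 and 2 are not separated. Nor do the documents support any effect on ORR, type I error or power.

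The conclusion rests on the protocol text alone. It assumes that no other study document given to sites contains a hold rule.

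**What to change.** In Section 5.2.2.3, state:

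> If a patient newly develops this pattern, or worsens to it from baseline, hold MGCD265 immediately, promptly repeat the liver tests and evaluate the cause. Discontinue permanently unless the repeat shows that the result was spurious, or the work-up documents liver metastases, biliary obstruction or another clearly supported cause as defined in Section 8.2.1. In those cases the investigator may resume dosing in consultation with the Sponsor. Return to Grade 1 is not required where the abnormality is due to liver metastases.

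The last sentence matters because Sections 5.2.1 and 5.2.2 prompt consideration of permanent discontinuation when recovery or interruption exceeds 3 weeks. A strict recovery rule could cost treatment in patients whom 5.2.2.3 now excuses.

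Make the stop sentence in Section 8.2.1 refer to 5.2.2.3. Leave the SAE reporting text as it is. Add a note under Table 8 that 5.2.2.3 takes precedence when bilirubin is ≥ 2 × ULN and alkaline phosphatase is < 2 × ULN.

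The cost is wording in two sections and one table note. The few affected patients would have a dose interruption, usually short, and a repeat local chemistry that the 8.2.1 work-up already implies. This is a cheap improvement.

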5.3 Medication Error

Medication errors may involve patient exposure to a wrong study drug, at a wrong dosing frequency, or at a wrong dose level (e.g., a dose that is not planned in the study). Medication errors occurring during the conduct of this study will be documented as AEs (regardless of whether clinical signs or symptoms are observed) and if serious consequences are observed, will be reported on Serious Adverse Event (SAE) forms. In all cases of medication error, the sponsor should be notified immediately.

5.4 Concomitant Therapies

5.4.1 Concomitant Medication(s)

Concomitant medications must be locally-approved and used at doses and regimens that are considered standard of care.

Treatment for co-morbidities, disease signs and symptoms and treatment emergent adverse events should be provided as necessary in the judgment of the investigator. Patients may continue to use any ongoing medications not prohibited by the inclusion/exclusion criteria or treatment plan. Supportive medication (e.g., antiemetics, analgesics, anti-diarrheals, etc.) is permitted.

Prophylactic anti-diarrheal medication may be administered at the discretion of the investigator as described in Section 5.2.2.1.

Antibiotics and analgesics should be used as needed. Patients with neutropenic fever or infection should be treated promptly. Therapeutic colony-stimulating factors should be used in accordance with American Society for Clinical Oncology guidelines. Packed red blood cell and platelet transfusions may be administered as clinically indicated.

5.4.2 Concomitant Surgery or Radiation Therapy

The use of surgery or radiation to manage cancer lesions during study treatment can jeopardize assessment of the primary objective of the study, evaluation of disease status; thus where clinically justified and possible, such treatment should be undertaken prior to study enrollment.

Although bleeding events have been reported with MGCD265 treatment, there have been no reported bleeding complications following surgical procedures performed in subjects treated with MGCD265. Significant inhibition of the VEGF receptor (VEGFR) pathway is not expected with MGCD265. For patients requiring surgery while on-study, MGCD265 dosing should be held for 3-7 days prior to any applicable procedure when possible, and treatment should be re-initiated once adequate closure or healing of the surgical site is established.

Any foreseeable need for palliative radiotherapy should be addressed before study entry, if possible and clinically appropriate (e.g., bone lesions at risk for spontaneous micro-fractures or painful lesions). However, these treatments may be used on-study where it is medically necessary. For patients requiring radiation while on-study, MGCD265 should be interrupted during the period that the patient is receiving radiation treatment.

5.4.3 Other Anticancer or Experimental Therapy

Use of approved or investigational anticancer treatment will not be permitted during the study treatment period, including chemotherapy, biological response modifiers, hormone therapies or immunotherapy. No other investigational drug may be used during treatment on this protocol. Concurrent participation in another therapeutic clinical trial is not allowed.

6 STUDY ASSESSMENTS

6.1 Screening

Voluntary, written, dated, and signed informed consent must be obtained before any study specific procedures are performed. Patients who completed the informed consent process but did not enroll on the study will be considered as screen failures. Limited information will be recorded in the CRF for these patients.

6.2 Study Period

For details on procedures during the study period, see Schedule of Assessments as shown in Table 2.

6.3 End of Treatment Assessment

All patients will be followed for adverse events and serious adverse events for at least 28 days following the last dose of MGCD265. See the Schedule of Assessments (Table 2) for evaluations to be performed at the End of Treatment visit.

6.4 Long-Term Follow-up and End of Study Assessment

Patients will be followed for survival at two month intervals as outlined in the Schedule of Assessments (Table 2). Treatments received following participation in the study will be collected in the CRF.

6.5 Patient Discontinuation/Withdrawal

Patients may discontinue from study treatment or from the study at any time at their own request, or they may be discontinued at any time at the discretion of the investigator or Sponsor for safety, behavioral reasons, or the inability of the patient to comply with the protocol required schedule of study visits or procedures at a given study site.

Criteria that may be used to discontinue patients from receipt of study medication will include, but will not be limited to:

- Objective disease progression according to RECIST 1.1 as determined by the investigator (patients who may derive clinical benefit may continue on treatment at the discretion of the investigator);
- Global deterioration of health status requiring discontinuation;
- Adverse event;
- Significant protocol violation;
- Lost to follow-up;
- Refusal for further treatment;
- Study termination by Sponsor;
- Pregnancy;
- Death.

Reasons for discontinuation from study follow-up may include:

- Study terminated by Sponsor;
- Lost to follow-up;
- Refusal for further follow-up for survival;
- Death.

If a patient does not return for a scheduled visit, every effort should be made to contact the patient. At least 2 attempts should be made to contact the patient, and each attempt should be recorded in the source documents. In any circumstance, every effort should be made to document patient outcome, if possible. The investigator should inquire about the reason for withdrawal, request that the patient returns for a final visit, and if applicable, follow-up with the patient regarding any unresolved adverse events.

If the patient withdraws from the study treatment and also withdraws consent for disclosure of future information, no further evaluations should be performed, and no additional data should be collected. The Sponsor may retain and continue to use any data collected before such refusal for further follow-up.

7 PROCEDURES

Every effort should be made to ensure that the protocol required tests and procedures are completed as described. However it is anticipated that there may be circumstances outside of the control of the investigator that may make it unfeasible to perform a protocol-specified assessment. In these cases the investigator will take all steps necessary to ensure the safety and well-being of the patient. When a protocol required test cannot be performed, the investigator will document in the source document and CRF the reason and any corrective and preventive actions which he/she has taken to ensure that normal processes are adhered to as soon as possible. The study team will be informed of these incidents in a timely fashion.

7.1 Molecular Testing for *MET* Mutations and Amplifications

To be eligible for enrollment, patients must have documented evidence of a genetic tumor alteration activating *MET*.

7.1.1 Genetic Tumor Alterations Required for Study Entry

Presence of an eligible *MET* gene alteration is defined as follows:

1. *MET* Mutations (based on human genome **GRCh37**/hg19 assembly and *MET* reference sequence NM_000245):
 - *MET* mutations that result in the alternative splicing or selective deletion of *MET* exon 14 as determined by gene sequencing or ribonucleic acid (RNA)-based reverse transcription polymerase chain reaction (qRT-PCR) analysis indicating:
 - point mutations involving c2888 or c3028 splice sites (or equivalent according to analytical reference standard), or
 - insertion or deletion mutations involving or proximal to c2888 or c3028 splice sites (or equivalent according to analytical reference standard), and/or
 - selective deletion of *MET* exon 14
 - *MET* activating mutations including but not limited to, P991S, Y1003F, Y1003N, Y1003*, V1070E, V1070R, V1092L, H1094L, H1094Y, H1094R, H1106D, M1131T, T1173I, V1188L, L1195V, V1220I, D1228H, Y1230C, Y1230H, Y1230D, Y1235D, Y1235H, M1250T.
 - Please note that these mutations have an alternative nomenclature based on GRCh37/hg19 assembly and *MET* reference sequence NM_001127500 as follows: P1009S, Y1021F, Y1021N, Y1021*, V1088E, V1088R, V1110L, H1112L, H1112Y, H1112R, H1124D, M1149T, T1191I, V1206L, L1213V, V1238I, D1246H, Y1248C, Y1248H, Y1248D, Y1253D, Y1253H, M1268T.
2. *MET* Gene Amplification in tumor tissue defined by any of the following:
 - Loose or tight clusters of *MET* too numerous to count as determined by *MET* 2-color fluorescent in situ hybridization (FISH)
 - *MET*/CEP7 ratio of > 5.0 in > 10% of evaluated cells as determined by *MET* 2-color FISH
 - Greater than or equal to 10 copies of *MET* per nucleus as determined by *MET* 2-color FISH
 - Greater than 8 copies in an appropriate molecular assay (DNA sequencing-based platform).

For ctDNA based analysis, a positive result for *MET* mutation or gene amplification by the Sponsor-provided central laboratory (Guardant) is required.

The method used to establish eligibility and the result will be documented in the patient's site source documents and the CRF.

